# Cabergoline for Lactation Inhibition After Early Second-Trimester Abortion or Pregnancy Loss: A Randomized Controlled Trial

Study Protocol and Statistical Analysis Plan

NCT06029673

October 24, 2023

**Title:** Cabergoline for Lactation Inhibition after Early Second-Trimester Abortion or Pregnancy Loss: A randomized controlled trial

**Investigators:** [REDACTED], MD MS; [REDACTED], MD MS

**Non-technical summary:** Breast pain following second-trimester abortion is common. Breast engorgement and milk leakage following second-trimester perinatal loss and abortion can cause both physical pain and emotional distress. Dopamine agonists have previously been shown to be effective in lactation inhibition for third-trimester fetal/neonatal loss or contraindications to breastfeeding. Our own prior work demonstrated that compared to placebo, a single dose of cabergoline was effective in preventing breast symptoms after abortion or loss 18-28 weeks. As lactogenesis starts as early as 16 weeks gestation, we hope to determine the efficacy of cabergoline earlier in the second trimester, 16-20 weeks.

We will conduct a double-blinded, placebo-controlled, gestational-age stratified superiority trial of those undergoing abortion or intrauterine fetal demise between 16 and 20-weeks gestation at Stanford Health Care. Participants will be randomized to either cabergoline 1 mg or placebo the day of procedure. Participants will complete a survey to assess symptoms, using the validated Bristol Breast Symptoms Inventory, and side-effects at baseline and Day 2, 4, 7, and 14 after the procedure. Our primary outcome is breast symptoms on Day 4 based on term lactation physiology. Secondary outcomes include satisfaction, acceptability, and side-effects. We plan to recruit 72 subjects powered to detect a 45% decrease in those reporting breast symptoms compared to the control group.

This study has the potential to improve overall patient experience by validating the routine use of cabergoline for lactation inhibition in the early second-trimester after abortion or pregnancy loss.

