## Specific aims

Lactogenesis is a two-stage physiologic process of developing the ability to secrete milk that starts in the 16th week of pregnancy and continues after delivery, peaking at day 4 postpartum, regardless of the birth outcome (1). Breast pain following second-trimester abortion is common (2). Breast engorgement and milk leakage following second-trimester perinatal loss and abortion can cause both physical pain and emotional distress (3). Dopamine agonists have previously been shown to be safe and effective in lactation inhibition for third-trimester fetal/neonatal loss or for those with contraindications to breastfeeding (4). Our own research recently found that among those seeking abortion care or management of fetal demise 18-28 weeks gestation, significantly fewer people who received a single dose of cabergoline reported any breast symptoms compared to placebo (5). Fewer than 1% of abortion nationally occur this late in pregnancy; most free-standing clinics provide abortion care for those less than 20 weeks. In our original study, we were underpowered to specifically make claims about those 18-20 weeks, and those 16-18 weeks were excluded. As there is biologic plausibility that lactogenesis starts as early as 16 weeks, this follow-up study seeks to determine if cabergoline is beneficial earlier in the second-trimester.

Therefore, we are hoping to answer whether cabergoline is superior to placebo at preventing symptomatic breast engorgement after early second-trimester abortion or loss. We will conduct a double-blinded, randomized, placebo-controlled, gestational-age stratified superiority trial of those undergoing abortion or intrauterine fetal demise between 16 and 20-weeks gestation at Stanford Health Care and evaluate the following aims:

**Aim 1** (Primary outcome). Determine if fewer pregnant people receiving cabergoline have breast symptoms post abortion/ post fetal expulsion compared to placebo. Participants will complete a survey to assess symptoms, using the validated Bristol Breast Symptoms Inventory at baseline and on days 2, 4, 7, and 14 post procedure. Based on physiology and prior symptom data, Day 4 will serve as our primary outcome.

**Aim 2** (Secondary outcomes). Determine if those receiving cabergoline report higher satisfaction, acceptability, and similar side-effects compared to placebo.

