### Day #0 – Pre-operative visit/Cervical preparation visit

Eligible patients who are scheduled for an abortion or are diagnosed with an intrauterine fetal demise between 16-20 weeks gestation will be approached to enroll in the study. A research staff member will obtain informed consent and randomization will occur. Basic demographic information will be collected and entered into REDCap by a research coordinator (10). Standard demographics, gender identity, prior breastfeeding/ chestfeeding experience, and prior breast surgery will be asked of participants. A baseline Bristol Breast

Inventory questionnaire will be performed to establish existing breast symptoms related to pregnancy followed by a 7-point Likert bother scale. Patients will be randomized and drug distributed (cabergoline or identical placebo) to be taken after the procedure on day #1.

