#### Days # 4-14 – Follow-up

Electronic, online surveys regarding breast symptoms using the Bristol Breast Inventory, and a 7-point Likert Scale to assess bother of symptoms and side effects will be collected on Days 2, 4, 7, and 14. Surveys will be sent via text message over RedCap at 08:00. A phone call will be made to participants between 17:00-20:00 if the survey is not completed that day.

An electronic gift card will be sent to the participant after 14 days. Participants will receive [REDACTED] per survey completed with a [REDACTED] bonus for completing all surveys on time for a maximum of [REDACTED] for full participation. With consent, the gift card will be distributed by e-mail or mobile phone number via Tango. Participants will have the opportunity to forego the gift certificate and donate funds to a reproductive health organization.

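### The summary promises a baseline side-effect survey that the visit schedule does not contain, which costs precision and interpretability on a secondary outcome

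*Combined protocol and SAP*

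**What the plan says.** All places are in the combined protocol and SAP.

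- **Non-technical summary.** One survey covers symptoms "and side-effects at baseline and Day 2, 4, 7, and 14 after the procedure".
- **Specific aims, Aim 1.** A baseline is tied to the breast inventory alone: "using the validated Bristol Breast Symptoms Inventory at baseline and on days 2, 4, 7, and 14 post procedure". Side-effects are not mentioned there.
- **Specific aims, Aim 2.** Side-effects are a secondary outcome, framed as a comparison of arms: "Determine if those receiving cabergoline report higher satisfaction, acceptability, and similar side-effects compared to placebo".
- **Day #0 section.** The history items are itemised: "Standard demographics, gender identity, prior breastfeeding/ chestfeeding experience, and prior breast surgery will be asked of participants". The only symptom measures are the breast inventory and a bother scale: "Inventory questionnaire will be performed to establish existing breast symptoms related to pregnancy followed by a 7-point Likert bother scale".
- **Days # 4-14 – Follow-up.** Side-effects appear here, on post-procedure days only: "a 7-point Likert Scale to assess bother of symptoms and side effects will be collected on Days 2, 4, 7, and 14".

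The study drug is handed out on Day #0 and taken at home after the procedure on Day #1. The Day #0 survey therefore precedes both procedure and dose.

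**The concern.** The two visit sections are what a coordinator would use to build the REDCap forms. Built from them, the forms would hold no side-effect data from before the dose, although the summary says they will.

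Participants are 16 to 20 weeks pregnant, and some may have general complaints on Day #0. The plan already accepts this reasoning for breast symptoms, where it takes a baseline because pregnancy itself can produce them. Without the same for side-effects, two things are lost. A complaint on Day 2 cannot be classed as new or long-standing for an individual. And if one arm happens to start with more complaints, the analyst cannot see it or adjust for it.

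This bears on Aim 2. The hoped-for answer is similarity to placebo, with no margin given and no side-effect analysis beyond the general wording under Data Management & Analysis. In that setting, noise makes a finding of no clear difference more likely.

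**Working it through.** The plan gives no figure on this point, so there is none to reproduce. The check is a comparison of texts, followed by illustrations of size.

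**Step 1: the schedule, side by side**

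| Place | Baseline side-effects? | Follow-up side-effects? |
|---|---|---|
| Non-technical summary | Yes | Days 2, 4, 7, 14 |
| Aim 1 | Not mentioned (breast inventory only) | Not mentioned |
| Day #0 section | No item listed | – |
| Follow-up section | – | Days 2, 4, 7, 14 |

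Only the summary names a baseline for side-effects.

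**Step 2: arm size**

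The plan recruits 72 and expects 10% missing data and loss. Assuming 1:1 allocation, that is 72/2 = 36 randomized per arm, and 72 × 0.9 / 2 = 32.4, so about 32 evaluable per arm.

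**Step 3: chance imbalance at baseline**

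Let p be the share with a complaint on Day #0. The documents do not give it, so 10% to 50% is assumed. The difference between arms has mean zero and SD = √(2p(1 − p)/n). For p = 0.20 and n = 36 this is √(0.32/36) = 0.094. The last two columns are exact, summed over two independent binomial counts.

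| p | SD of difference, n = 36 | Chance of ≥15 points, n = 36 | Chance of ≥15 points, n = 32 |
|---|---|---|---|
| 10% | 7.1 points | 3% | 6% |
| 20% | 9.4 points | 10% | 16% |
| 30% | 10.8 points | 16% | 22% |
| 50% | 11.8 points | 20% | 26% |

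Counts are whole numbers, so 15 points means at least 6 participants at n = 36 and at least 5 at n = 32. That explains part of the gap between the last two columns. The mean of zero shows that there is no expected bias.

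**Step 4: what a baseline would and would not recover**

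Assume true side-effect rates of 20% on cabergoline and 5% on placebo, and an independent background complaint rate b in both arms. All of these are assumptions.

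- Raw observed rate = 1 − (1 − b)(1 − true rate).
- Rate counting only new complaints = (1 − b) × true rate. This assumes that the background is exactly the Day #0 complaints and that they persist, which flatters the baseline.
- SE of the difference = √((p₁(1 − p₁) + p₂(1 − p₂))/32).

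| b | Counting rule | Rates | Difference | Ratio | SE |
|---|---|---|---|---|---|
| 20% | Raw | 36% vs 24% | 12 points | 1.5 | 11.4 points |
| 20% | New only | 16% vs 4% | 12 points | 4.0 | 7.3 points |
| 40% | Raw | 52% vs 43% | 9 points | 1.2 | 12.4 points |
| 40% | New only | 12% vs 3% | 9 points | 4.0 | 6.5 points |

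Counting new complaints leaves the difference where it was. It restores the ratio and shrinks the standard error.

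For a graded score, linear adjustment for baseline cuts the variance by r². An assumed correlation of 0.3 to 0.5 gives 9% to 25%, so the standard error is about 5% to 13% smaller (√0.91 = 0.954, √0.75 = 0.866).

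**The case against.** **The texts may not truly conflict.** The Day #0 section does not claim to be a complete list, and a section headed as follow-up would naturally name only follow-up days. The summary may be a lay compression of one survey schedule, and a side-effect before any drug is an odd idea. All of this is fair, and it means the investigators' intent cannot be settled from the text. It does not remove the need to reconcile the sections, because the forms will be built from one reading or the other.

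**The placebo arm already does the work.** A reader might infer that later side-effects cannot be told apart from complaints present before the dose, or that the arm comparison is biased towards similarity. The documents do not support either reading. Aim 2 compares arms in a randomized, double-blinded trial, so background complaints are balanced in expectation and the drug effect is separated at group level. What is lost is classification of the individual and control of chance imbalance.

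**A Day #0 survey misses the procedure.** Complaints caused by the procedure or induction arise after Day #0 and before or around the dose. No baseline at that visit can remove them; only the placebo arm can. This stands in full.

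**The shrinkage from 15 points to 9 is not the price of the missing baseline.** It is tempting to read it so. But Step 4 shows that counting only new complaints still gives 9 points, and every rate there is assumed. Nor do the documents say that every complaint on Day 2 would be counted as a side-effect: neither the items nor a counting rule is given.

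**Conclusion.** The inconsistency is real, and its consequence is limited. If the visit sections are followed as written, the trial will hold no pre-dose side-effect data for a named secondary outcome. Post-dose complaints then cannot be classed as new or pre-existing for individuals, and chance imbalance stays hidden. The probability of an imbalance of at least 15 points is 3% to 20% with 36 per arm, or 6% to 26% with 32. Both ranges rest on an assumed prevalence of 10% to 50% and on 1:1 allocation.

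The comparison with placebo stays unbiased in expectation. The loss is of precision and interpretability for side-effects only; the primary outcome, its own baseline and the sample size are unaffected. It is worth acting on because the remedy is cheap and a missed baseline cannot be collected afterwards.

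**What to change.** 1. Add the side-effect items used in the follow-up surveys to the Day #0 REDCap survey, and list them in the Day #0 section, so that it matches the summary.
2. In Data Management & Analysis, state that raw side-effect rates by arm are the main comparison. Beside them, report rates of complaints that are new or worse than at baseline, or a baseline-adjusted comparison, and tabulate baseline complaints by arm.
3. State that complaints arising from the procedure are handled by the placebo comparison, not by the baseline.

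The cost is a few items on an existing survey, about a minute more per participant at Day #0, and a few lines of analysis text. No more participants are needed.

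If the sponsor prefers not to collect a baseline, the summary should be corrected and the plan should say that side-effects are compared between arms without one. That is consistent with Aim 2, but it gives up the check on imbalance and the new-or-worse reporting.

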## Specific aims

Lactogenesis is a two-stage physiologic process of developing the ability to secrete milk that starts in the 16th week of pregnancy and continues after delivery, peaking at day 4 postpartum, regardless of the birth outcome (1). Breast pain following second-trimester abortion is common (2). Breast engorgement and milk leakage following second-trimester perinatal loss and abortion can cause both physical pain and emotional distress (3). Dopamine agonists have previously been shown to be safe and effective in lactation inhibition for third-trimester fetal/neonatal loss or for those with contraindications to breastfeeding (4). Our own research recently found that among those seeking abortion care or management of fetal demise 18-28 weeks gestation, significantly fewer people who received a single dose of cabergoline reported any breast symptoms compared to placebo (5). Fewer than 1% of abortion nationally occur this late in pregnancy; most free-standing clinics provide abortion care for those less than 20 weeks. In our original study, we were underpowered to specifically make claims about those 18-20 weeks, and those 16-18 weeks were excluded. As there is biologic plausibility that lactogenesis starts as early as 16 weeks, this follow-up study seeks to determine if cabergoline is beneficial earlier in the second-trimester.

Therefore, we are hoping to answer whether cabergoline is superior to placebo at preventing symptomatic breast engorgement after early second-trimester abortion or loss. We will conduct a double-blinded, randomized, placebo-controlled, gestational-age stratified superiority trial of those undergoing abortion or intrauterine fetal demise between 16 and 20-weeks gestation at Stanford Health Care and evaluate the following aims:

**Aim 1** (Primary outcome). Determine if fewer pregnant people receiving cabergoline have breast symptoms post abortion/ post fetal expulsion compared to placebo. Participants will complete a survey to assess symptoms, using the validated Bristol Breast Symptoms Inventory at baseline and on days 2, 4, 7, and 14 post procedure. Based on physiology and prior symptom data, Day 4 will serve as our primary outcome.

**Aim 2** (Secondary outcomes). Determine if those receiving cabergoline report higher satisfaction, acceptability, and similar side-effects compared to placebo.

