### *Research Design and General Methodological Approach*

The proposed study is similarly designed as a double-blinded, placebo-controlled, gestational-age stratified (16/0-17/6, 18/0-19/6 weeks gestation) superiority trial to evaluate cabergoline's role in relieving breast engorgement after second-trimester abortion or fetal demise. We will again capture breast symptoms using the validated Bristol Breast Inventory (9). A superiority design was selected as cabergoline is fairly expensive with possible side-effects. For this study to be practice-changing, cabergoline needs to demonstrate clear superiority over placebo.

The use of cabergoline for lactation inhibition after a third trimester delivery has been clearly established (4). Our own work has recently been presented and published, leading to inclusion of cabergoline into more clinical protocols more in the late second trimester (5). The aim of this study is to establish cabergoline's benefit in the early second trimester – a more common experience among pregnant people. As many free-standing, independent clinics only offer abortion care to 19 weeks 6 days gestation, we want to ensure that there is evidence for using cabergoline in our broader community.

We estimate that 15 subjects in each gestational-age strata (16/0-17/6 and 18/0-19/6 weeks gestation) are required to show a 45% decrease in those reporting breast symptoms compared to the control group, with a power of 0.8 and an alpha of 0.05. We plan to recruit 72 subjects, anticipating 10% missing data and loss to follow up.

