#### *Data Management & Analysis*

Stanford University has a license for the RedCap data management system (10). REDCap is a web-based application that is secure, reliable, and HIPAA-compliant for storing research study data. REDCap is designed with built-in features to address confidentiality and compliance requirements. Electronic, online surveys will be sent via text message over RedCap on Days 2, 4, 7, 14. Data associated with patient health identifiers (PHI), including the signed informed consent, will be collected electronically. REDCap allows for easy data download into SAS or other statistical software programs. No data will be collected on paper forms. SAS OnDemand will be used for data analysis. Data will be analyzed with parametric or non-parametric statistical tests, as

appropriate. Stratified analysis and logistic regression will be performed to assess demographic characteristics as predictors of breast symptoms and associated distress.

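### Aim 2 sets out to show similar side-effects, but the plan has no criterion for similarity and names only generic tests, so it cannot support that conclusion

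*Combined protocol and SAP*

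**What the plan says.** Specific aims, Aim 2, gives the secondary objective: "Determine if those receiving cabergoline report higher satisfaction, acceptability, and similar side-effects compared to placebo". The non-technical summary lists the same outcome without a direction: "Secondary outcomes include satisfaction, acceptability, and side-effects".

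The sample-size statement, in Research Design and General Methodological Approach, concerns breast symptoms alone. It says 15 subjects per gestational-age stratum "are required to show a 45% decrease in those reporting breast symptoms compared to the control group, with a power of 0.8", and then: "We plan to recruit 72 subjects, anticipating 10% missing data and loss to follow up". The same section explains the choice of design: "A superiority design was selected as cabergoline is fairly expensive with possible side-effects".

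On measurement, the summary says the survey covers "side-effects at baseline and Day 2, 4, 7, and 14 after the procedure". The follow-up section describes "a 7-point Likert Scale to assess bother of symptoms and side effects will be collected on Days 2, 4, 7, and 14". This could mean a bother score that covers side-effects, or side-effects recorded separately.

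On analysis, Data Management & Analysis says: "Data will be analyzed with parametric or non-parametric statistical tests", chosen as appropriate. The stratified analysis and logistic regression named there are for demographic predictors of breast symptoms and distress, not for comparing side-effects between arms.

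**The concern.** Concluding that two arms have similar side-effects needs a statement of how large a difference would still count as similar, and an interval or test judged against it. The plan gives neither, and does not say that the comparison is descriptive. The only stated tool is a test of difference, and failing to reject no difference is not evidence of similarity.

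The risk is that a null test in roughly 32 to 36 people per arm gets reported as similar side-effects when the data are also compatible with a sizeable excess on cabergoline. The plan itself names possible side-effects as a reason for demanding superiority, and it hopes to support routine use. An unsupported reassurance on side-effects would feed into that recommendation.

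**Working it through.** **What the plan's sample size covers.** The control rate behind the figure of 15 is not stated. Take 97.0%, the placebo rate in the prior trial (Preliminary work), and read the 45% decrease as relative, so p1 = 0.97 and p2 = 0.97 × 0.55 = 0.5335. The pooled two-sided formula is

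n = [1.96·√(2p̄(1−p̄)) + 0.842·√(p1(1−p1) + p2(1−p2))]² / (p1−p2)².

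With p̄ = 0.752 this is (1.197 + 0.444)² / 0.4365² = 14.1, so 15 per arm in each stratum. An absolute decrease (97% to 52%) gives 14. The figure is therefore reproduced as a breast-symptom calculation; nothing in it refers to side-effects. Four cells of 15 make 60, and 60/0.9 = 67 rather than 72. That step is unexplained but does not matter here; 72 is used below.

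**Inputs for side-effects.** From the documents: 72 recruited, 10% loss. Assumed, because the documents do not say: 1:1 allocation, a two-sided 5% test, the side-effect rates, and the 10- and 20-point benchmarks. Evaluable per arm: 72 × 0.9 / 2 = 32.4, taken as 32; with no loss, 36.

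**1. Precision, yes/no side-effects, equal rates p.** Half-width of the 95% interval = 1.96·√(2p(1−p)/n).

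| p | n = 32 | n = 36 |
|---|---|---|
| 5% | 10.7 points | 10.1 |
| 10% | 14.7 | 13.9 |
| 20% | 19.6 | 18.5 |
| 30% | 22.5 | 21.2 |
| 50% | 24.5 | 23.1 |

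**2. Chance that a true 20-point excess is non-significant** (pooled z test; exact enumeration of the uncorrected chi-square test in brackets).

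| Placebo vs cabergoline | n = 32 | n = 36 |
|---|---|---|
| 5% vs 25% | 39% (34%) | 33% (29%) |
| 10% vs 30% | 48% (47%) | 43% (42%) |
| 20% vs 40% | 59% (58%) | 54% (53%) |
| 30% vs 50% | 63% (61%) | 59% (59%) |

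The first row is rough because events are few.

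**3. Chance that the interval rules out an excess of m when the true rates are identical.** Φ(m/√(2p(1−p)/n) − 1.96).

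| p | m = 10 points, n = 32 | n = 36 | m = 20 points, n = 32 | n = 36 |
|---|---|---|---|---|
| 5% | 45% | 50% | 96% | 97% |
| 10% | 27% | 29% | 76% | 81% |
| 50% | 12% | 13% | 36% | 40% |

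The normal approximation is optimistic at 5%. Summing binomial probabilities over all outcomes for which the upper Newcombe limit falls below m gives about 25% (n = 32) and 35% (n = 36) for 10 points, and about 81% and 89% for 20 points.

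**4. If side-effects are a 7-point score compared by means**, the percentage-point figures do not apply. Half-width = t(0.975, 2n−2)·√(2/n) = 0.50 SD at 32 per arm and 0.47 SD at 36. A true excess of 0.5 SD is non-significant about 50% and 45% of the time (two-sample t test).

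**The case against.** The strongest reply is that this rests on one word in a one-sentence secondary aim. The summary words the same outcome neutrally, the plan never mentions equivalence or non-inferiority, and nowhere does it say that a non-significant p-value will be read as similarity. Trials are normally sized on the primary outcome, so not sizing for side-effects is no fault in itself. The plan does not exclude confidence intervals, and the team's prior trial reported its breast-symptom domains as risk ratios with them. The magnitudes depend on assumed rates and on an assumed form of the endpoint.

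Much of this stands and limits the weight of the point. The aim is secondary, the misreading is a risk rather than a stated rule, sizing on the primary outcome is ordinary practice, and the figures are ranges under assumptions. If side-effects are rare, the trial could rule out a large excess.

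It does not remove the point. The aim is to determine similarity, and the plan gives no basis for doing so. How breast symptoms were reported in an earlier trial does not pre-specify anything for side-effects here. The favourable rare-event case would be visible only if an interval were reported.

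**Conclusion.** The concern holds. As written, the analysis plan cannot deliver the side-effect conclusion that Aim 2 seeks: nothing defines similarity, and the generic tests named cannot establish it. That conclusion follows from the text and needs none of the assumed rates.

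The assumed rates bear only on size. With 32 to 36 per arm, a null result would leave differences of roughly 10 to 25 percentage points open, or about half a standard deviation on a score. From a 10% placebo rate upward, a true 20-point excess would go undetected about 4 to 6 times in 10.

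This should be corrected, but it concerns a secondary aim and does not touch the Day 4 primary analysis.

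**What to change.** Reword the side-effect part of Aim 2 to: *estimate the difference in side-effects between cabergoline and placebo*. This also brings it into line with the neutral wording of the non-technical summary.

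In Data Management & Analysis, add that the between-arm difference will be reported with a 95% confidence interval for the side-effect measures the survey already collects: a risk difference if they are yes/no, a difference in scores if they are on the 7-point scale. If events are few, an interval that behaves well at low rates, such as Newcombe's, is preferable to the simple normal one. State that a non-significant difference will not be read as similarity.

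The cost is one reworded aim and a few sentences of analysis text, with no added participants, visits or survey items. The downside is a weaker claim: an estimated difference with its uncertainty, rather than a statement that side-effects are similar.
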